#### 9 INVESTIGATIONAL PLAN

# 9.1 Overall Study Design and Plan

This study is a multicenter, open-label, efficacy and safety study of pegloticase in combination with MTX in adult subjects with uncontrolled gout.

The study design will include: 1) up to a 2-week Screening Period (screening should be complete within 2 weeks prior to Week -4), 2) a 4-week MTX Run-in Period (Week – 4 through Day 1); 3) a 52-week Pegloticase + IMM (Pegloticase + MTX) Period 4) a Safety Follow-up (Phone/Email/Site Visit) and 5) a 3 and 6 month Post Treatment Follow-up.

All subjects who meet eligibility criteria at Screening will begin oral MTX at a dose of 15 mg weekly for 4 weeks prior to the first dose of pegloticase.

Subjects will also take folic acid 1 mg orally every day beginning at Week -4 (the start of MTX) and continuing until prior to the Week 52 Visit. Subjects must be able to tolerate MTX at a dose of 15 mg during the MTX Run-in (Week -4 through Day 1) to be eligible to participate in the Pegloticase + IMM Period. Subjects who are unable to tolerate MTX at a dose of 15 mg during the MTX Run-in Period will be considered screen failures.

Subjects who take at least one dose of MTX and who are females of childbearing potential, will receive a safety follow-up Phone Call/E-mail/Site Visit approximately 30 days after the last dose of MTX to verify at least one ovulatory cycle has occurred after the last dose of MTX. If the subject has not ovulated, a urine pregnancy test will be performed. Subjects who receive at least one dose of MTX and who are non-vasectomized males, will be asked, 3 months after MTX discontinuation, regarding partner pregnancy.

Protocol: HZNP-KRY-201 Version 3.0, Adminstrative Change 1

KRYSTEXXA IND: 010122

All subjects who complete the Run-In Period will receive the first pegloticase infusion on Day 1. All subsequent doses and study visits will be scheduled based on the Day 1 visit date.

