# 9.3.2 Exclusion Criteria

Subjects will be ineligible for study participation if they meet any of the following criteria:

- 1. Weight >160 kg (352 pounds).
- Any serious acute bacterial infection, unless treated and completely resolved with antibiotics at least 2 weeks prior to the Week -4 Visit of the Screening/MTX Run-in Period.
- 3. Severe chronic or recurrent bacterial infections, such as recurrent pneumonia or chronic bronchiectasis.

Protocol: HZNP-KRY-201

KRYSTEXXA IND: 010122

Version 3.0, Adminstrative Change 1

4. Current immunocompromised condition, including current or chronic treatment with systemic immunosuppressive agents, including prednisone >10 mg/day or equivalent dose of other corticosteroid.

- 5. History of any transplant surgery requiring maintenance immunosuppressive therapy.
- 6. Known history of hepatitis B virus surface antigen positivity or hepatitis B DNA positivity.
- 7. Known history of hepatitis C virus RNA positivity.
- 8. Known history of Human Immunodeficiency Virus (HIV) positivity (tested at Screening Visit).
- 9. Glucose -6-phosphage dehydrogenase (G6PD) deficiency (tested at the Screening Visit).
- 10. Severe chronic renal impairment (glomerular filtration rate <25 mL/min/1.73 m^2) or currently on dialysis.
- 11. Non-compensated congestive heart failure or hospitalization for congestive heart failure within 3 months of the Screening Visit, uncontrolled arrhythmia, treatment for acute coronary syndrome (myocardial infarction or unstable angina), or uncontrolled blood pressure (>160/100 mmHg) at the end of the Screening/MTX Run-in Period.
- 12. Pregnant, planning to become pregnant, breastfeeding, planning to impregnate female partner, or not on an effective form of birth control, as determined by the Investigator.
- 13. Prior treatment with pegloticase (KRYSTEXXA), another recombinant uricase (rasburicase), or concomitant therapy with a polyethylene glycol-conjugated drug.
- 14. Known allergy to pegylated products or history of anaphylactic reaction to a recombinant protein or porcine product.
- 15. Contraindication to MTX treatment or MTX treatment considered inappropriate.
- 16. Known intolerance to MTX.
- 17. Receipt of an investigational drug within 4 weeks or 5 half-lives, whichever is longer, prior to MTX administration at Week -4 or plans to take an investigational drug during the study.

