- 18. Current liver disease, as determined by alanine transaminase or aspartate transaminase levels >3 times upper limit of normal at the Screening Visit.
- 19. Currently receiving systemic or radiologic treatment for ongoing cancer, excluding non-melanoma skin cancer.
- 20. History of malignancy within 5 years other than non-melanoma skin cancer or in situ carcinoma of cervix.
- 21. Uncontrolled hyperglycemia with a plasma glucose value >240 mg/dL at screening that is not subsequently controlled by the end of the Screening/MTX Run-in Period.
- 22. Diagnosis of osteomyelitis.

KRYSTEXXA IND: 010122 Protocol: HZNP-KRY-201 Version 3.0, Adminstrative Change 1

23. Known history of hypoxanthine-guanine phosphoribosyl-transferase deficiency, such as Lesch-Nyhan and Kelley-Seegmiller syndrome.

- 24. Unsuitable candidate for the study, based on the opinion of the Investigator (e.g., cognitive impairment), such that participation might create undue risk to the subject or interfere with the subject's ability to comply with the protocol requirements or complete the study.
- 25. Alcohol use in excess of 3 alcoholic beverages per week.
- 26. Currently receiving allopurinol and unable to discontinue medication 7 days prior to MTX dosing at Week -4 and unable to discontinue treatment during the duration of the study.

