### 9.4.6.3.2.2 MTX Dose Titration Algorithm and Intolerance Criteria

During the MTX Run-in a subject will be considered a screen failure if any of the following new laboratory findings or symptoms reflecting MTX intolerance occur:

PRIVATE AND CONFIDENTIAL INFORMATION OF HORIZON THERAPEUTICS IRELAND DAC

Page 57 of 129

- 1. Abnormal Hematology findings:
  - a. WBC  $< 3.5 \times 10^9/L$
  - b. Platelets  $< 75 \times 10^9/L$
  - c. Hematocrit < 32%
- 2. Abnormal hepatic function findings:
  - a. AST/ALT >1.5 x upper limit of reference range and
  - b. Albumin < lower limit of reference range
- 3. Abnormal renal function: eGFR <40ml/min/1.73 m^2 (as estimated with the MDRD equation).
- 4. New clinically important signs and symptoms, such as the following:
  - a. Rash or oral ulceration
  - b. Persistent nausea, vomiting and diarrhea
  - c. New or increasing dyspnea or dry cough, or unexplained cough with fever
  - d. Severe sore throat, abnormal bruising
  - e. Severe headaches, fatigue, and problems concentrating

Note that if minor clinical symptoms emerge, such as mild stomatitis, mild GI discomfort, etc., the investigator may increase folic acid dose (e.g. 2 mg daily) or recommend a divided dose of MTX (e.g. 3 tabs of 2.5 mg in the morning and evening on the day of dosing); if symptoms improve, subject will not be considered a screen failure on the basis of that symptom.

During the Run-In and Pegloticase+IMM Period, MTX dose guidance based on new laboratory findings or new symptoms is as follows:

Lab Parameters	Value	MTX Dose Change
WBC	$3.0 \times 10^9/L \sim 3.5 \times 10^9/L$	Decrease to 10 mg
	< 3.0 x 10  /L	Temporary stop
Platelets	< 50 x 10  /L	Temporary stop
Hematocrit	< 27%	Temporary stop
AST/ALT	Between 1.5 ~ 2 x ULN	Decrease to 10 mg
	> 2 x ULN	Temporary stop
eGFR	< 30 ml/min/1.73 m 	Temporary stop
New clinically important symptoms/signs*	Yes	Temporary stop

\* New clinically important symptoms or important medical events:

KRYSTEXXA IND: 010122

- a. Rash or oral ulceration
- b. Persistent nausea, vomiting and diarrhea
- c. New or increasing dyspnea or dry cough, or unexplained cough with fever
- d. Severe sore throat, abnormal bruising
- e. Severe headaches, fatigue, and problems concentrating

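### Entry limits admit subjects to MTX 15 mg weekly at eGFR 25–29 or AST/ALT above 2 to 3 × ULN, inside the protocol's own stop range for undefined new findings

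*Protocol*

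**What the plan says.** Protocol Section 9.3.2 sets two numeric limits that bear on MTX safety. Exclusion 10 reads "Severe chronic renal impairment (glomerular filtration rate <25 mL/min/1.73 m"² or dialysis. Exclusion 18 removes subjects with ALT or AST "levels >3 times upper limit of normal at the Screening Visit". Two further exclusions rest on judgement without a number: exclusion 15 ("Contraindication to MTX treatment or MTX treatment considered inappropriate") and exclusion 24, for unsuitable candidates in whom "participation might create undue risk to the subject".

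Section 9.1 states: "All subjects who meet eligibility criteria at Screening will begin oral MTX at a dose of 15 mg weekly". No reduced starting dose is given for impaired renal or liver function.

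Section 9.4.6.3.2.2 contains two sets of limits. The first makes a subject a run-in screen failure if "any of the following new laboratory findings or symptoms reflecting MTX intolerance occur"; this list includes eGFR below 40, and AST/ALT above 1.5 × ULN together with low albumin. The second is a dose table, introduced by "During the Run-In and Pegloticase+IMM Period, MTX dose guidance based on new laboratory findings or new symptoms is as follows". Its only eGFR row is a temporary stop at "< 30 ml/min/1.73 m"². For AST/ALT it cuts the dose to 10 mg between 1.5 and 2 × ULN and sets a temporary stop above 2 × ULN. The section then lists triggers for discussion with the medical monitor. One is ALT/AST above 1.5 × ULN on 3 of any 5 consecutive measures; another is a finding that has led to a temporary stop on 3 consecutive measures.

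**The concern.** A subject can satisfy both numeric entry limits and start MTX at full dose with a renal or liver value that the same protocol treats as a reason to stop MTX once treatment has begun. What happens next depends on the word *new*, for which Section 9.4.6.3.2.2 gives neither a reference visit nor a size of change.

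At stake is the safety of individual subjects and uniform handling across sites. Two sites facing the same subject could act differently: one continues 15 mg weekly because the value was present at entry, and the other holds MTX or screen-fails the subject for an abnormality that was known before the first tablet.

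**Working it through.** No published figure needs to be reproduced; the check compares thresholds. I assume that GFR in exclusion 10 is the MDRD estimate used in Sections 9.4.6.3.2.2 and 9.5.4.7.

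| | eGFR (mL/min/1.73 m²) | AST/ALT |
|---|---|---|
| Excluded at entry (9.3.2) | <25 | >3 × ULN at Screening |
| Dose cut to 10 mg (9.4.6.3.2.2) | none | 1.5–2 × ULN |
| Temporary stop (9.4.6.3.2.2) | <30 | >2 × ULN |
| Run-in screen failure (9.4.6.3.2.2) | <40 | >1.5 × ULN with low albumin |
| Medical-monitor review (9.4.6.3.2.2) | only after a stop on 3 consecutive measures | >1.5 × ULN on 3 of any 5 measures |

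**Overlap of entry range and action range**
- Renal, stop value: eligible ≥25, stop <30. Overlap 25 to <30, width 30 − 25 = 5 units.
- Renal, run-in failure: eligible ≥25, failure <40. Overlap 25 to <40, width 40 − 25 = 15 units.
- Liver, stop value: eligible ≤3 × ULN, stop >2 × ULN. Overlap above 2 and up to 3 × ULN.

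**Renal, if *new* exempts pre-MTX values.** A subject entering at eGFR 27 is already below the only eGFR row, so no lower value is named at which to act. An investigator may regard a further fall to 20 as new, but nothing says how large a fall counts. The monitor trigger cannot help on this parameter, because it needs earlier stops and the exemption means none occurred. The subject takes all four run-in doses, 4 × 15 = 60 mg, and weekly dosing continues.

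**Renal, if it does not exempt them.** The same subject meets the stop value and also the run-in failure limit of 40. So does anyone entering at 30–39, for the failure limit alone. The first scheduled on-MTX chemistry is at Week -2 (Section 9.5.4.7), so up to two scheduled doses (Weeks -4 and -3), 2 × 15 = 30 mg, come first.

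**Liver, if *new* exempts pre-MTX values.** Above 2 × ULN is the highest row, so no dose action is stated for a subject entering at, say, 2.5 × ULN. The 3-of-5 review trigger still works. If pre-MTX draws count, Screening, Week -4 and Week -2 give three qualifying measures by Week -2. If only on-MTX draws count, Week -2, Day 1 and Week 2 give the third at Week 2. The trigger leads to a discussion and fixes no dose change.

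**Liver, if it does not exempt them.** MTX is held. The re-escalation guidance requires enzymes at or below 1.5 × ULN, which a subject whose usual value is 2.5 × ULN may never reach. Inclusion 8, which requires four weeks of 15 mg tolerated, then comes into doubt.

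**The case against.** The best defence is that the two sets of limits answer different questions. Entry limits define who may join; the table and the failure list address deterioration on drug, are expressly confined to new findings, and in the failure list to findings that reflect intolerance. A value known before the first dose is neither. This stands in one respect: a reader might infer that the protocol contradicts itself, and it does not. The point is a mismatch between limits, made unsafe by an undefined word.

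A reader might also infer that liver values have no backstop. The review trigger at 1.5 × ULN defeats that reading, so the liver half is the lesser point.

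Section 9.6.5 defines baseline as the last non-missing observation before MTX, and the adverse-event definitions speak of change from baseline. Both suggest the right reference visit. They sit in other sections, however, and neither gives the size of worsening that should change a dose.

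Eligibility is re-confirmed at Week -4, Week -2 and Day 1, exclusions 15 and 24 are available, and MTX may be reduced or stopped after Day 1. These are real safeguards, but at eGFR 25–29 re-checking exclusion 10 still returns eligible, and the others depend on judgement.

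Finally, defining *new* alone would supply an action rule without narrowing eligibility. That is true. It would still allow 15 mg weekly to begin at a value the protocol itself uses to stop the drug.

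**Conclusion.** The point holds as a mismatch between entry and dosing limits. The bands admitted past a stop value are eGFR 25 to <30 and AST/ALT above 2 and up to 3 × ULN. The renal half is the main one: on one reading there is no eGFR action value or review trigger for these subjects, and on the other everyone entering at 25–39 is screen-failed after avoidable exposure. On the liver side, what is missing is a stated dose action, since monitor review remains.

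This rests on exclusions 15 and 24 not being applied to such a subject, and on GFR being measured in the same way at entry and on treatment. The protocol does not say how many of the planned 12–16 subjects would fall in these bands; there may be none. A reader might infer a bias in the Month 6 response rate or its denominator. The documents give no basis for that, and none is claimed. The change should be made on safety and consistency grounds.

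**What to change.** Change exclusion 10 to eGFR <30 and exclusion 18 to AST/ALT >2 × ULN, in Section 9.3.2 and in the synopsis, so that the entry limits match the stop values.

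In Section 9.4.6.3.2.2, for values still admitted within an action band (eGFR 30–39 for the run-in failure rule, AST/ALT 1.5–2 × ULN for the 10 mg cut), define *new* as a stated worsening from the last pre-MTX value. Add that the stop values, eGFR <30 and AST/ALT >2 × ULN, apply whatever the entry value was.

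The cost is one amendment. No tests are added, since chemistry is already drawn at Screening, Week -4, Week -2 and Day 1. Eligibility becomes slightly narrower, by a number the protocol does not give. The change will not catch every case: Screening may be up to two weeks before Week -4, and MTX is dispensed at the same visit as the Week -4 draw, so a value can move before that result is known.

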- f. Any other important medical events that might increase methotrexate toxicity or pre-dispose to new or worsening infection (e.g. undergoing surgery, hospitalization, being treated with antibiotics, having a clinical infection, developing new clinically significant pericardial / pleural effusion or ascites)

Note that if minor clinical symptoms emerge, such as mild stomatitis, mild GI discomfort, etc., the investigator may increase folic acid dose to 2 mg daily or recommend a divided dose of MTX (e.g. 3 tabs of 2.5 mg in the morning and evening on the day of dosing) and monitor for symptom resolution.

Investigators should discuss the emergence of any one of the following criteria with the medical monitor to review the case:

- 1.  $ALT/AST > 1.5 \times ULN$  on 3 of any 5 consecutive measures
- 2. Albumin < 0.8 x LLN on 2 consecutive measures
- 3. Any laboratory or clinical symptoms leading to temporary stop on 3 consecutive measures, in which case the medical monitor will review to consider re-initiation, a continued temporary stop, or a permanent stop in discussion with the PI.

Guidance for increasing MTX back towards 15 mg after dose reduction, based on improvement or resolution of abnormal liver enzymes (>2 × upper limit of normal):

- 1. When liver enzymes return to values ≤1.5 × upper limit of normal, increase MTX or dose by 2.5 mg and reassess in 2 weeks.
- 2. If liver enzymes remain ≤1.5 × upper limit of normal, increase MTX or dose by 2.5 mg and reassess in 2 weeks.

Improvement of other laboratory abnormalities potentially attributed to MTX or may also warrant titration back up to 15 mg weekly, based on PI judgement and in discussion with the Sponsor medical monitor.

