# 9.5.4.7 Clinical Laboratory Safety Tests

Blood (for hematology and clinical chemistry) and urine (for uric acid:creatinine ratio) samples will be collected at the Screening, Week -4 (prior to the first dose of MTX), and Week -2 Visits during the Screening/MTX Run-in Period; prior to pegloticase infusion on Day 1 and at the Weeks 2, 6, 14, 22, 24 and 36, Visits during the Pegloticase + IMM Period; and the non-infusion End of Pegloticase Infusions Visit (if applicable), Week 52/End of Study/Early Termination and 3 and 6 month Post Treatment Follow-up Visits.

Safety laboratory assessments will include:

- Hematology: complete blood count with differential (hemoglobin concentration, hematocrit, erythrocyte count, platelet count, leukocyte count, and differential leukocyte count)
- Chemistry: albumin, transaminases (aspartate aminotransferase, alanine aminotransferase), alkaline phosphatase, total bilirubin, creatinine (including calculation for eGFR calculated by the abbreviated MDRD equation : creatinine (including calculation for eGFR calculated by the MDRD study equation: 175 x (Scrfmg/dL1)-1.154 x (age) $^{-0.203}$ x (0.742 if female) x (1.212 if African American) or 175 x ( $S_{erfumol/L}/88.4$ ) $^{-1.154}$ x (age)-0.203x (0.742 if female) x (1.212 if African American), glucose, sodium, potassium, calcium, chloride, total protein, blood urea nitrogen, and human chorionic gonadotropin (at the Screening Visit for all female subjects of childbearing potential)
- Urine: uric acid:creatinine ratio and human chorionic gonadotropin (at all visits except the Screening Visit for all female subjects of childbearing potential)

Safety laboratory samples will be analyzed by the central laboratory. Samples will be collected for analysis at the local laboratory, if needed.

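### Section 9.4.6.3.2.2: the methotrexate re-escalation guidance names the liver-enzyme tier for which the dose table orders a temporary stop, not a reduction, and gives no starting dose after a stop

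*Protocol*

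**What the plan says.** Section 9.4.6.3.2.2 of the Protocol holds both parts of the rule.

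- **Dose table** (run-in and Pegloticase + IMM Period). For AST/ALT the lower tier is "Between 1.5 ~ 2 x ULN", with the action "Decrease to 10 mg". The upper tier is above 2 times ULN, with the action "Temporary stop".
- **Re-escalation guidance.** It is introduced as "Guidance for increasing MTX back towards 15 mg after dose reduction", and the same sentence ties it to abnormal liver enzymes above 2 times ULN ("after dose reduction, based on improvement or resolution of abnormal liver enzymes (>2 × upper limit of normal"). Step 1 reads "When liver enzymes return to values ≤1.5 × upper limit of normal, increase MTX or dose by 2.5 mg", with reassessment after 2 weeks. Step 2 reads "If liver enzymes remain ≤1.5 × upper limit of normal, increase MTX or dose by 2.5 mg and reassess in 2 weeks".

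Two neighbouring clauses also matter. Re-initiation after a temporary stop is mentioned only as a medical monitor review, when findings leading to a stop occur on 3 consecutive measures. A closing paragraph leaves titration back to 15 mg to investigator judgement in discussion with the medical monitor, but only for laboratory abnormalities other than liver enzymes.

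**The concern.** The table treats a reduction and a stop as different actions and assigns each to its own liver tier. The guidance speaks of recovery from a reduction but identifies it by the enzyme level that triggers a stop. A site handling a subject who went above 2 times ULN and has recovered must then guess the dose to which the first 2.5 mg is added. A site handling a subject who was reduced to 10 mg at 1.5 to 2 times ULN finds no liver-specific instruction at all.

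This is an operative safety instruction for the drug that the trial adds to pegloticase. Sections 9.1, 9.4.1 and 9.4.6.3.1.2 all send sites to it when MTX is not tolerated. What is at stake is uniform handling of the same liver event across about 8 centers.

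**Working it through.** The plan states no figure to reproduce here. The check matches the tiers and then does the step arithmetic.

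**Inputs, all from section 9.4.6.3.2.2 except the starting dose**

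- Starting MTX dose: 15 mg weekly (section 9.4.6.3.1.2).
- Table action at 1.5 to 2 times ULN: decrease to 10 mg.
- Table action above 2 times ULN: temporary stop, taken here as 0 mg while stopped.
- Re-escalation: two listed increases of 2.5 mg, each conditional on enzymes at or below 1.5 times ULN.

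**Step 1: match the tiers**

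| AST/ALT tier | Action in the table | Named in the re-escalation guidance? |
|---|---|---|
| 1.5 to 2 times ULN | Reduction to 10 mg | No |
| Above 2 times ULN | Temporary stop | Yes, but described as a reduction |

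The guidance and the table disagree about the action taken above 2 times ULN.

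**Step 2: apply the listed increases**

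Dose after both increases = starting dose + 2 × 2.5 mg.

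- From 10 mg: 10 + 5 = 15 mg.
- From 0 mg: 0 + 5 = 5 mg, which is 15 − 5 = 10 mg below 15 mg.
- Steps needed from 0 mg to 15 mg: 15 / 2.5 = 6. Two are listed.
- From the 15 mg taken before a stop: 15 + 5 = 20 mg, above the level the guidance aims at, so the pre-stop dose cannot be the intended starting point.

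The two listed steps fit the 10 mg tier exactly, and that is the tier the parenthesis leaves out.

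**Step 3: look for another clause that fills the gap**

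- The medical monitor review of re-initiation needs 3 consecutive measures. A subject who is stopped once and has recovered at the next test does not reach it.
- The closing paragraph on investigator judgement covers only other laboratory abnormalities.
- Neither clause gives a restart dose after a single liver-related stop. Neither supplies a liver-specific path back from 10 mg.

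**The case against.** The strongest defence is that this is labelled guidance and can be read loosely. A dose reduction may be meant to include a stop. The guidance aims only in the direction of 15 mg and does not promise to reach it. Step 2 ends with a further reassessment, so it may be meant to repeat. All of this is fair, and it means that ending at 5 mg after two steps is not in itself a contradiction. It does not remove the mismatch: the table separates the two actions, the text does not say that step 2 repeats, and on any reading the starting dose after a stop is missing.

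A reader might infer more than this. The documents do not support the following:

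- **That the table could raise a dose in a subject already below 10 mg.** The action is worded as a decrease, and a site would not read that as an increase. Repeated AST/ALT above 1.5 times ULN on 3 of any 5 consecutive measures also goes to the medical monitor.
- **That reassessment after 2 weeks conflicts with the chemistry schedule.** Section 9.5.4.7 schedules tests in the treatment period at Day 1 and at "Weeks 2, 6, 14, 22, 24 and 36, Visits during the Pegloticase + IMM Period", which are mostly further apart than 2 weeks. The run-in visits at Week -4, Week -2 and Day 1 are 2 weeks apart, however, infusion visits are every 2 weeks, and the section allows local laboratory samples if needed.
- **That a site could resume at 15 mg after a liver-related stop.** No liver text says so; both listed steps are 2.5 mg increases.
- **That the primary response rate would shift by a stated amount.** Nothing in the Protocol links the pace of re-escalation to response or says how many subjects would be affected. Section 9.1 already accepts varying MTX exposure, because the dose may be reduced or discontinued after Day 1 and the subject may stay in the study.

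**Conclusion.** The concern holds as an internal contradiction in a dosing instruction. Above 2 times ULN the table orders a stop, while the guidance describes a reduction. The listed increases reach 15 mg from 10 mg but 5 mg from a stop. No starting dose is given after a stop, and the tier that is reduced has no liver-specific route back.

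The tier mismatch and the missing starting dose rest on the text alone. The 5 mg figure assumes that a stop means 0 mg and that the two listed steps are not repeated. The practical consequence is that sites acting in good faith could re-dose MTX differently after the same event. How often that would happen cannot be estimated from the Protocol, and no sample-size or analysis figure is affected. The point should be corrected because it sits in a safety rule for the drug under test and costs little to settle.

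**What to change.** The sponsor should reconcile the dose table and the re-escalation guidance in section 9.4.6.3.2.2 so that three things agree: the liver-enzyme tier named in the guidance, the action the table assigns to that tier, and the dose from which the increases start. It should also be clear which text applies to the other tier. Which thresholds, actions and doses are correct is for the sponsor to decide.

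The cost is a few lines of amendment text in one section and a note to sites. It needs no new visits and no change to the sample size or the analysis.
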